### Secondary Objectives:

1. Evaluate the antiviral efficacy of treatment with oseltamivir compared with placebo in those subjects with confirmed influenza infection (primary efficacy population) and intention to treat (ITT) population as assessed by the following parameters:

Virologic: (by PCR in NP swab)

- AUC of viral shedding
- Duration of viral shedding
- Percent cessation of viral shedding on Days 3 and 7
- Frequency of emergence of antiviral resistance

Clinical:

- Time to alleviation of influenza clinical symptoms
- Time to absence of fever
- Time to resolution of all symptoms AND fever
- Time to resumption of normal activity
  - Note: in this analysis, this objective will be assessed by:
    - Time to feeling as good as before the onset of the influenza illness (as measured by a global assessment question)
    - Time to return to pre-influenza illness level of function (as measured by a global assessment question)
    - Time to return to pre-influenza illness level of physical function (as measured by SF-36 physical score)
- Proportion of subjects who require hospitalization
- Proportion of subjects who develop bronchitis, pneumonia, or other complications of influenza

2. Evaluate the association of viral shedding (both qualitative and quantitative) to clinical symptoms and fever.

3. Evaluate if changes in viral shedding by antiviral treatment predict changes in clinical symptoms and fever.

4. Evaluate subject self-collected nasal samples compared with study team collected samples for the determination of viral shedding.

5. Evaluate the variability in the sample collection. (pilot study only) [NOTE: This is not addressed in this SAP]

## **Endpoints:**

### **Primary Endpoint**

Percentage of subjects shedding virus by PCR in NP swab at day 3.

### **Secondary Endpoints**

#### Clinical Endpoints:

- Time to alleviation of influenza clinical symptoms
- Time to absence of fever
- Time to resumption of normal activity
  - Note: in this analysis, the following endpoints will be used to represent “resumption of normal activity”:
    - Time to feeling as good as before the onset of the influenza illness (as measured by a global assessment question)
    - Time to return to pre-influenza illness level of function (as measured by a global assessment question)
    - Time to return to pre-influenza illness level of physical function (as measured by SF-36 physical score)
- Number of premature study treatment discontinuations
- Proportion of subjects who develop bronchitis, pneumonia, or other complications of influenza
- Proportion of subjects who require hospitalization
- 28-day mortality

Virologic Endpoints: (assessed by PCR in NP swab)

- Duration of viral shedding
- Change in viral shedding as a function of time
- AUC of viral shedding
- Frequency of emergence of antiviral resistance

## 1 General analysis considerations

Unless otherwise specified, data summaries and analyses will be presented overall and by randomized arm.

To help protect participant confidentiality, listings of individual patient level data will be minimized as much as possible. Dates will also not be presented in listings; instead, for example, listings will present details as days since randomization.

## 2 Application validation

All study-specific programs for creation of derived datasets for derivation of the endpoint defined in this document will require application validation and verification per written Standard Operating Procedures as appropriate.

## 3 Visit and Evaluation Schedule

The expected schedule for clinic visits (per protocol) is shown in **Table 1** below. To allow for possible deviations from these, the visit windows have been expanded for analysis purposes as indicated. If there are multiple measurements within a window, then the one closest to the scheduled time will be used in analysis.

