6 STUDY PROCEDURES

The following table (Table 4) outlines all of the assessments to be conducted during the study. A detailed presentation of assessments immediately follows the table. Total volumes of blood drawn are noted in the text for each study day. Details regarding the research samples (tubes, swabs, etc) will be detailed in the Manual of Procedures. The day when the subject is enrolled and randomized is denoted as Study Day 0, the first day after randomization is Study Day 1, etc.

Table 4: Schedule of Assessments

| Day +/- Window Evaluation/Procedure | Screen | Baseline | | | | | |
|--|---------------|-----------------|--------|--------|---|-------|--------|
| | -1 to 0 | 0 | 1 Home | 2 Home | 3 | 7 ± 1 | 28 ± 3 |
| ELIGIBILITY | | | | | | | |
| Informed consent | X | | | | | | |
| Demographics | X | | | | | | |
| Medical history | X | | | | | | |
| Site influenza testing (PCR or rapid Ag, See Section 7.2.2) | X | | | | | | |
| RANDOMIZATION/ STUDY DRUG | | | | | | | |
| Randomize subject | | X | | | | | |
| Dispense Study Treatment Kit | | X | | | | | |
| STUDY PROCEDURES | | | | | | | |
| Review and collect diary card (see Section 7.3.1) | | X ¹ | | | X | X | X |
| Assess for complications of influenza (see Section 7.3.2) | | X | | | X | X | X |
| Vital signs, including SaO ₂ (see Section 7.3.3) | X | X | | | X | X | X |
| Assessment of study drug compliance (see Section 7.5) | | | | | X | | |
| Review of concomitant medications | | | | | X | X | X |
| Physical exam ² (see Section 7.1.2) | X | | | | X | X | X |
| Adverse events | | | | | X | X | X |
| SAFETY LABORATORY | | | | | | | |
| Urine βHCG (for females of childbearing potential) | X | | | | | | |
| REFERENCE PROCEDURE | | | | | | | |
| Nasopharyngeal swab for virus isolation | | X | | | X | X | |
| Subject sample self-collection (see Section 6.3.3.2) | | X | X | X | X | | |
| Stored Serum | | X | | | X | X | X |

Notes: 1. On Day 0, subject will be instructed on how to complete the diary card, and baseline assessment will be collected.

2. Brief physical examinations will be conducted at screening to ensure there are not medical conditions (either chronic or acute) that would increase a subject's risk for participation in this study. Symptom-targeted physical examinations will be conducted at all other visits as needed to evaluate new complaints and possible adverse events.

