6.3.3.4 Study Day 0: Study Drug Distribution

The study drug kit will be distributed to the subject, with instruction on how to take each dose every 12 hours. Treatment should begin as soon as possible. However up to 24 hours is permitted between enrollment (signing consent) and the first dose of study medication. To ensure timely administration of the first dose of the study medication, it may be taken in the research facility/ clinic. The time that the first dose is taken should be recorded.

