##### 4.8.1 Primary Endpoint [IRCRSLT] (population for the primary analysis and PEP)

The primary endpoint is defined as the percentage of subjects shedding virus by PCR in nasopharyngeal swabs obtained at Day 3.

- a. Completeness of viral shedding results showing number (%) at Day 0, 3 and 7 who:
  - had qPCR result
  - were lost to follow-up prior to the visit
  - were in follow-up but had missing value
- b. Primary Analysis: Among subjects with Day 3 qPCR results, number (%) with detectable viral shedding at Day 3. Comparison of randomized arms with associated 95% confidence interval and p-value based on the normal approximation to the binomial distribution.

- c. Sensitivity Analyses (PEP only): to assess potential impact of missing measurements. Repeat the primary analysis (above) considering missing measurements in turn as (a) above the limit of detection, or (b) below the limit of detection, or (c) above the limit of detection in one randomized arm and below in the other arm (so as to maximize the difference between arms), or (d) the opposite of (c) (so as to minimize the difference between arms).
- d. Sensitivity Analyses (PEP only): Repeat the primary analysis above but restricted (a) to samples in which one or more housekeeping genes had detectable levels (hence indicating adequate sample); and (b) to samples in which all housekeeping genes had detectable levels.
- e. Subgroup Analyses (PEP only): Comparison of randomized treatments will be undertaken by sex (male vs female), influenza type (A vs B), and country/race (US/white vs US/non-white vs Thailand vs other countries). To assess whether the difference between randomized treatments varies by subgroup, a treatment by subgroup interaction test will be undertaken using logistic regression.

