#### **4.10 Evaluation of self-collected samples (PEP and ITT)**

Self-collected NP are collected on Day 0 (prior to treatment initiation), Day 0 evening, Day 1, Day 1 evening, Day 2, Day 2 evening and Day 3. Viral shedding will be assessed using these self-collected swabs by the same assay used for the team collected swabs, i.e., quantitative RT-PCR (reported as  $\log_{10}$  RNA copies/mL).

- a. Completeness of viral shedding results showing number (%) at Day 0, Day 0 evening, Day 1, Day 1 evening, Day 2, Day 2 evening and Day 3 who:
  - had swab taken (i.e. submitted)
  - had qPCR result
  - died prior to visit
  - were lost to follow-up prior to the visit
  - were in follow-up but had missing value
- b. Among subjects with Day 3 qPCR results, number (%) with detectable viral shedding at Day 3. Comparison of randomized arms with associated 95% confidence interval and p-value based on the normal approximation to the binomial distribution. This table can be compared to table 4.8.1a, the primary endpoint, to determine if the self-swabs would have similar treatment effects
  - Repeat analysis in the population for the primary analysis (PEP excluding pilot study) to allow direct comparison with primary endpoint.
- c. Bland-Altman plot showing the agreement between the result from the self-collected swabs and team-collected swabs across all available swabs
- d. Bland-Altman plot showing the agreement between the result from the self-collected swabs and team-collected swabs on Day 0 and Day 3.
- e. Table: Mean, standard deviation, median, min, max, 25% and 75% percentiles of the viral load difference between self-collected swabs and team-collected swabs on Day 0, Day 1, Day 2 and Day 3. P-values comparing the difference based on normal approximation or Wilcoxon signed rank test, as appropriate for the data.
- f. Plots of associations between viral load based on self-collected swabs and viral load based on team-collected swabs on Day 0, Day 1, Day 2 and Day 3. Spearman correlation coefficients, along with their 95% confidence intervals, will be provided. Plots of associations and estimated correlation coefficients will be provided both over all subjects and by strata defined by quartile of the viral load based on team-collected swabs at each time point.

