- g. AUCs will be calculated for the self-collected swabs. This is defined as the area below the line formed by joining the measured values at each successive scheduled measurement time and above the limit of detection. This will be calculated using the trapezoidal rule. Missing values will be ignored (this is equivalent to imputing a missing value using linear interpolation between the previous and succeeding available values). If the Day 0 value is missing, then the subject will be excluded from the analysis.
  - Figure and associated table showing number of subjects and minimum, maximum, median, 25% and 75% percentile of the value of viral shedding at each scheduled measurement time. This will be presented (a) imputing values

as defined above for the calculation of AUC, and (b) using observed values only.

- Table showing number of subjects and minimum, maximum, median, 25% and 75% percentile of the AUC, both over all subjects and by strata defined by quartile of Day 0 measurement.
- P-value comparing randomized arms from Wilcoxon rank sum test stratified by quartile of Day 0 measurement.

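### SAP Table 1 lets a Day 2 home self-swab stand in for a missing Day 3 self-swab, and the Days 2 to 4 window for the primary NP swab goes unchecked

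*SAP*

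**What the plan says.** The column headings of protocol Table 4 (section 6) read "1 Home | 2 Home | 3 | 7 ± 1 | 28 ± 3": Days 7 and 28 carry a tolerance and Day 3 does not. SAP section 3 then says: "To allow for possible deviations from these, the visit windows have been expanded for analysis purposes as indicated". In SAP Table 1 the analysis window for Day 3 is 3±1, while Day 1 (Home) and Day 2 (Home) keep single-day windows of 1 and 2. There is one selection rule: "If there are multiple measurements within a window, then the one closest to the scheduled time will be used in analysis". Nothing says which swab type the wider window covers, or that a sample may serve only one visit.

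The primary endpoint in SAP 4.8.1 is the "percentage of subjects shedding virus by PCR in nasopharyngeal swabs obtained at Day 3", analysed as "Among subjects with Day 3 qPCR results, number (%) with detectable viral shedding at Day 3". The sensitivity analyses listed there deal with missing results and with housekeeping-gene detection.

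For self-swabs, SAP 4.10 lists a pre-treatment Day 0 sample and then "Day 0 evening, Day 1, Day 1 evening, Day 2, Day 2 evening and Day 3"; the protocol (3.1 and 7.3.4.5) has one sample a day on Days 0 to 3. For the self-swab AUC, 4.10g states: "Missing values will be ignored (this is equivalent to imputing a missing value using linear interpolation between the previous and succeeding available values").

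**The concern.** Two separate matters follow from the same table.

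**Self-swabs.** Day 2 belongs to two analysis windows. A subject with a Day 2 home swab and no Day 3 self-swab would, by the stated rule, have the Day 2 value reported under both days. Comparing self-collected with team-collected samples is a secondary objective (protocol 2.2, item 4), and the comparison means little if the two samples were taken on different days. Where virus is clearing, an earlier swab is more likely to be positive, so the error has a direction: self-swabs would look more positive than team swabs.

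**Primary NP swab.** An NP swab from an early or late visit, Day 2 or Day 4, counts as Day 3. The planned tables do not show how many results are of this kind or whether they differ by arm, and no analysis is limited to swabs taken on Day 3 itself. If visit timing were related to recovery, and so to treatment, the comparison could be biased.

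**Working it through.** **1. The overlap.** Day 2 (Home) = {2}; Day 3 = 3±1 = {2, 3, 4}; the shared day is {2}. Table 1 does reach self-swabs: in protocol Table 4 the only procedure marked under the two Home columns is self-collection, and SAP section 3 gives diary cards a separate rule. For a subject with a Day 2 self-swab but none on Day 3 or 4:

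- Day 2 result: the Day 2 swab.
- Day 3 result: the only candidates are the Day 2 swab and, if taken, the evening one listed in SAP 4.10. One is selected.
- 4.10b: it counts as Day 3 in the table meant for comparison with the primary endpoint.
- 4.10d–f: the Day 3 pair is a Day 2 self-swab against the team swab of the Day 3 visit.
- 4.10g: Day 3 is the last scheduled point, so no later value exists to interpolate towards. Ignoring it ends the curve at the last available swab; filling it carries the Day 2 level forward. The two rules give different AUCs.

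**2. The plan's own figures.** Protocol 9.2.1 assumes 42.5% vs 57.5%, 90% power and a two-sided 5% Fisher test. At 245 per arm (490 in total) exact Fisher power is 0.903. Then 490/0.9 = 544.4, so 545, or 546 as an even total. The stated 490 and 546 reproduce.

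**3. Primary endpoint, under assumptions.** The primary efficacy population (PEP) is PCR-positive at Day 0 (SAP 4.1), so 100% detectable. The pooled Day 3 figure is 50% (protocol 9.2.1), assumed here to apply to the PEP. The average fall is (100 − 50)/3 = 16.7 points per day. The shape is not given, so two are used: linear, p(t) = 1 − (1 − p₃)t/3, and exponential, p(t) = p₃^(t/3).

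| | Day 2 | Day 3 | Day 4 |
|---|---|---|---|
| Pooled % detectable, exponential | 63.0 | 50.0 | 39.7 |
| Pooled % detectable, linear | 66.7 | 50.0 | 33.3 |
| Arm difference, exponential (points) | 12.6 | 15.0 | 15.9 |
| Arm difference, linear (points) | 10.0 | 15.0 | 20.0 |

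Evaluable subjects: 510 × 0.9 = 459, or n = 229.5 per arm. Power by the normal approximation is Φ[(d√n − 1.96√(2p̄(1−p̄))) / √(p₁(1−p₁)+p₂(1−p₂))]. With all swabs on Day 3: (0.15 × 15.149 − 1.96 × 0.7071)/0.6991 = 1.27, power 0.898.

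| Swabs off Day 3 (same in both arms) | Power |
|---|---|
| None | 0.898 |
| 10% Day 2 and 10% Day 4 | 0.892–0.898 |
| 20% Day 2 and 20% Day 4 | 0.885–0.898 |
| 20% Day 2 only | 0.855–0.879 |
| 20% Day 4 only | 0.905–0.933 |

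Timing that differs by arm, with no true effect and 10% on Day 2 in one arm against 10% on Day 4 in the other: 0.10 × (63.0 − 39.7) = 2.3 points (exponential) and 0.10 × (66.7 − 33.3) = 3.3 points (linear).

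**4. Self-swabs, under assumptions.** Shift = share filled from Day 2 × fall from Day 2 to Day 3. If self-swabs follow the same path, the fall is 13.0 to 16.7 points. A 10% share gives 1.3 to 1.7 points; shares of 5% and 20% give 0.7–0.8 and 2.6–3.3. If viral load falls 1 log10 per day (range 0.5–1.5), a 10% share moves the mean self-minus-team difference by 0.1 log10 (0.05–0.15).

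**5. Time on treatment.** Days count from randomization, yet protocol 6.3.3.4 says: "However up to 24 hours is permitted between enrollment (signing consent) and the first dose of study medication". With illustrative clock times, a first dose at 15:00 on Day 1 and a swab at 09:00 on Day 2 gives 18 h; a first dose at 09:00 on Day 0 and a swab at 17:00 on Day 4 gives 104 h. With the same times but Day 3 swabs only, the range is 42 to 80 h. So 80 − 42 = 38 of the 104 − 18 = 86 h would remain without the wider window.

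**The case against.** The best defence is that SAP section 3 introduces the windows for clinic visits, so 3±1 is naturally the tolerance of the Day 3 clinic visit. SAP 4.10 names its time points and counts missing values at each, and 4.10g has its own rule, which as the more specific one should govern. This stands as far as intent goes: the authors may never have meant a home swab to serve as Day 3. But Table 1 includes the Home days, the nearest-to-schedule rule has no exception, and 4.10b and 4.10d–f contain no rule that would override it. A programmer following the text could do exactly this.

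On the primary endpoint more of the defence stands. A reader might infer that a self-swab can become the primary result. It cannot: the endpoint is defined on NP swabs, and self-swabs are analysed separately (SAP 4.3.5, 4.10). No NP swab is scheduled on Day 2, so one would need an early visit, and a true Day 3 swab is preferred whenever one exists. A reader might also infer that the endpoint is seriously distorted because shedding falls fast, so that a one-day shift matches the 15-point target. The documents give no Day 2 or Day 4 rates, and a shift of every swab is not a difference between arms. Nor is the 18 to 104 h range caused by the window alone; part of it is dosing delay, which should balance under blinded randomization, and SAP 4.3.3c already tabulates time from randomization to first dose.

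Widening analysis windows is common, and excluding off-day NP swabs from the main analysis would only add missing data.

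**Conclusion.** The self-swab point holds as a specification error on a literal reading: a stated rule can yield a wrong-day pairing, double use of one sample, and a conflict with 4.10g. Its size depends on how many Day 3 self-swabs are missing, which the documents do not give.

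The primary-endpoint point holds only as an unchecked choice. NP swabs from Days 2 to 4 are accepted although the protocol gives Day 3 no window, and no listed analysis tests this. The effect on the treatment comparison is probably small: about 1 point of power at most when off-day swabs are few and balanced between early and late, and more if they all fall early. A false difference of 2 to 3 points would need timing to differ by arm. All of these sizes rest on the assumed path of decline and the assumed off-day shares. The documents do not support saying that the primary result is biased or that 3±1 must be abandoned.

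**What to change.** In SAP section 3 and Table 1:

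- Assign each sample to one visit only, and state that a scheduled Day 1 or Day 2 home self-swab may not serve as Day 3.
- Let the Day 3 self-swab follow the actual Day 3 clinic visit. Protocol 6.3.6.2 lists the NP swab and the self-swab at the same visit, so a visit held on Day 4 should keep both. Limiting self-swabs to calendar Day 3 would break that matched pair.
- In 4.10, pair self and team swabs only when taken on the same calendar day.
- Reconcile the evening self-swabs in SAP 4.10 with the once-daily schedule in the protocol.

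For the primary endpoint, keep 3±1 for the NP swab. Add to 4.8.1 a sensitivity analysis, in the population for the primary analysis, limited to NP swabs taken on actual Day 3. Tabulate by arm the study day of the swab and the hours from first dose to swab.

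The cost is SAP wording, one extra table and one extra model run, with no new data collection. A few Day 3 self-swab values become missing. The primary analysis is unchanged.

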**Table 1. IRC003 Study days and analysis windows**

Visit	Days since randomization					
	Day 0 (Baseline*)	Day 1 (Home)	Day 2 (Home)	Day 3	Day 7	Day 28
Per protocol (Days)	0	1	2	3	7±1	28±3
Analysis (Days)	0 (-1 if 0 not available)	1	2	3±1	7±2	28±7

\* *Baseline evaluation must be completed prior to the first dose of study medication.*

For the diary cards, the auto-populated study day ('stday') on the CRF will be used to select the measurements at each time point. If there are multiple measurements within a window, the calculated study day (i.e. date of evaluation - randomization date), will be used to choose the one closest to the scheduled time.

#### 4 Analysis Plan

Unless otherwise stated, all tables and figures will show results by randomized arms.

Throughout this analysis plan, annotations in square brackets ([XXX]) provide the source table/view names and, in some cases, target fields in the IRC004 database.

Per protocol, at study entry, results from laboratory tests obtained for clinical indications within 24 hours before randomization may be used if available.

Unless otherwise stated, data will be presented in tables. For tables with categorical variables, the number (%) will be presented. For tables with continuous variables, the mean, standard deviation, median, 25th and 75th percentiles, min and max will be presented. The number with missing values will also be shown. In calculation of percentages, subjects with missing data will not be included in the denominator. Data presented as listings or figures noted.

##### 4.1 Analysis Populations

All tables and figures will note the analysis population used:

- Enrolled Population includes all subjects who had a signed informed consent form for screening.
- Intention To Treat (ITT) Population includes all subjects who were randomized and who received at least one dose of study drug (as defined in Section 7.2.1 of the protocol).
- Primary Efficacy Population (PEP) includes subjects in the ITT population with influenza infection confirmed in central laboratory testing. Given the virology needed to analyze the primary endpoint, this is defined as having an influenza virus isolated and typed in the qualitative PCR evaluation at Day 0 from central laboratory testing (or Day -1 if Day 0 not available).
- The population for the primary analysis is defined as the subgroup of the PE Population that excludes the subjects who participated in the pilot study (because efficacy results for those subjects were used in selecting the primary endpoint for the study).

